1 BACKGROUND

Ventricular tachycardia (VT) is a life threatening rhythm disturbance of the heart, which is associated with a significant risk of mortality as well as morbidity. VT is particularly prevalent in patients with ischaemic heart disease. Over the past three decades, catheter directed ablation has emerged as an increasingly useful adjunct to the implantable cardioverter-defibrillator (ICD) as treatment for this rhythm disorder, especially if medications fail, or are prohibited by side effects or patient choice. Traditional catheter ablation of VT uses several different invasive mapping methods to analyse the ventricular myocardium in detail and aims to modify those areas which are thought to be critical for sustaining the arrhythmic circuit. Commonly used techniques include activation mapping, entrainment mapping, pace-mapping and substrate mapping.

Activation mapping is a technique which, in cases of focal VT, records the earliest ventricular activation to find areas which are key in the generation of the arrhythmia, or in cases of re-entrant VT, to identify the diastolic pathway which allows the perpetuation of the arrhythmia¹.

Entrainment mapping is a technique whereby critical parts of the arrhythmia circuit can be identified by pacing at different locations, in an attempt to enter the excitable gap and capture the arrhythmia circuit. Once the critical isthmus utilised by the circuit is identified, ablation in this area can lead to termination of the arrhythmia.²

Both activation and entrainment mapping require a stable VT which is haemodynamically tolerated, which is often not the case. Therefore other methods of invasively mapping VT have been devised, most notably substrate mapping. Substrate mapping can be performed with the patient in sinus rhythm and is based on the fact that arrhythmogenic substrate in the ventricle produces different EGM signals from healthy tissue. Features of interest include fractionated signals, low voltage, split or double potentials, mid-diastolic potentials, late potentials and locally abnormal ventricular activity (LAVA)^{3,4}.

For some patients, particularly in those with non-ischaemic cardiomyopathy, scar is predominantly epicardial or mid-myocardial, meaning that endocardial mapping and ablation may be of limited efficacy⁵. In these cases, accessing the epicardium via a subxiphoid incision and performing additional ablation on the epicardial surface has been shown to be of benefit^{6,7}.

Recently, data have emerged suggesting that computational modelling of a patient's heart based on 3D MRI reconstructions can enable prediction of optimal targets for VT ablation non-invasively. This has been confirmed in both retrospective and prospective studies.⁸ This involves high resolution MRI imaging with late-gadolinium enhancement (LGE) to assess the three-dimensional geometry of the scar, followed by reconstruction of the patient's heart *in silico*^{9,10}. Fibre orientation is established and overlaid onto this model¹¹. Standard electrophysiological properties are applied to the different categories of tissue as defined by the LGE signal intensity, namely, normal tissue, scar and grey zone. Using computational modelling, this "virtual heart" is then analysed for different potential ventricular tachycardia circuits that are theoretically sustainable based on the information supplied. A virtual electrophysiology study with programmed stimulation is conducted by virtually pacing the heart model from various different locations⁹. An algorithm is used to predict optimal ablation sites to terminate all possible VT circuits in this model heart. The algorithm initially generates "primary sites", which are the initial locations which have the potential to sustain ventricular tachycardia in the patient's heart. The model then undergoes virtual VT ablation of these primary sites and the prediction algorithm is re-run. This may generate a new VT-sustaining substrate and give predictions of "secondary sites" which can sustain VT in the post-ablation heart. The process is repeated until the heart is no longer VT-inducible.¹². In this way, not only should the patient's clinical VT be ablated, but all future potential ventricular tachycardias supportable by the substrate in its current form should also be avoided, reducing the need for repeat VT ablation.

2 RATIONALE

Current invasive substrate mapping techniques are time and labour intensive. The ability to identify arrhythmogenic from non-arrhythmogenic areas within the same scar is limited, leading to prolonged procedure time and the potential overuse of ablative energy. Activation mapping during ventricular tachycardia, the gold standard for defining the critical isthmus sustaining the arrhythmia, is significantly limited by hemodynamic instability.

Image-guided VT ablation has been shown to improve substrate definition and may underpin improved outcomes in certain patient populations^{13,14}. Given the newly emerging field of personalised medicine and computation modelling this study will help to assess if an MRI-based, computer generated model accurately correlates to the invasive findings from an EP study with regards to targeting ablation in VT. If the model proves to be accurate, this will help to advance the process of *in silico* planning of VT ablation and potentially lead to improvements in outcomes of VT ablation, as well as reducing the need for repeated procedures. Results from the invasive studies can also be fed back into the computational model in an attempt to improve its accuracy. Furthermore, by assessing the electrophysiological properties of the computer generated predicted sites, we may learn which signals may indicate a critically important part of the VT circuit which traditional electroanatomical maps may miss.

3 THEORETICAL FRAMEWORK

As outlined above

4 RESEARCH QUESTION/AIM(S)

- To assess the accuracy of an MRI-based, computer-generated model of the heart in predicted sites which are particularly important in generating and sustaining ventricular tachycardia.
- What are the invasive electrophysiological properties of the sites which are predicted by the MRI-based computational model?
- Does ablation of the computer generated predicted sites lead to a change in the electrophysiological properties of distant sites?

4.1 Objectives

- To perform high resolution cardiac MRI prior to undergoing catheter-based VT ablation in order to non-invasively assess scar and provide data for computational modelling and prediction of likely VT circuits *in silico*.
- To assess the accuracy of the *in silico* predicted sites when compared to invasively obtained electrophysiological data.
- To assess the ventricular scar characteristics in patients with scar-dependent VT using high-definition invasive mapping.
- To invasively assess the *in silico* predicted sites in order to ascertain the electrophysiological properties which likely lead to their prediction as key sites for arrhythmogenesis.
- To corroborate the *in silico* predictions with the invasive findings during catheter-based VT ablation.

4.2 Outcome

- Assessment of the degree of validation of *in silico* computational modelling by invasive ventricular scar interrogation to see if the predicted sites match those sites which would have been determined as important from invasive mapping.
- Qualification of the electrophysiological characteristics of those sites which the computational model predicted in an attempt to see what it is about them that makes them likely to be key to maintaining the arrhythmia. With our mapping techniques, we can assess not only the amplitude and morphology

of the electrograms from these areas, but also the directionality of wavefronts to see if this is an important feature. With the additional benefit of the 3D computational model, we may be able to gain some insight into the 3D nature of channels which form part of the VT substrate.

- Assessment of the change in the invasive electrophysiological characteristics of distant sites following ablation of the primary predicted *in silico* sites. By ablating the predicted areas, it is possible that when we re-map distant points, they may be a change in their electrophysiological properties. There may be a change in variables such as the stim-QRS latency, the QRS morphology, the capture threshold and the nature of the exit site (e.g. multiple-exit site changing to single-exit site).
- Assessment of the frequency of ventricular arrhythmia, frequency of therapy delivered from an ICD (if applicable) and duration until first delivered therapy on serial heart rhythm monitors. Also assessment of patient's symptoms and adverse effects on clinical consultation.

5 STUDY DESIGN and METHODS of DATA COLLECTION AND DATA ANALYSIS

The study will be a single centre, prospective study based at St George's University Hospitals NHS Foundation Trust in London. Consecutive patients presenting to the hospital with an appropriate scar-dependent, sustained monomorphic ventricular tachycardia, requiring catheter ablation, will be screened for inclusion into the study. Full inclusion and exclusion criteria are listed below. Patients are likely to be predominantly outpatients, requiring elective VT ablation, however inpatients may also be included in the study.

If found eligible for the study, the patient will be approached by one of the study investigators and a Patient Information Sheet (PIS) will be offered. Written consent will be obtained if the patient is willing to proceed.

If included in the study, de-identified, anonymized MRI images from patient's routine scan will be transferred to Johns Hopkins University, Baltimore Maryland, for computational analysis. The patient's MRI images will be reconstructed, analysed and a 3D geometric model of the patient's heart formed. From this, a computer-generated model of the patient's heart will be created. As described above, a virtual EP study, VT ablation and generation of both primary and secondary sites will be generated. The computation model as well as the locations of these primary and secondary sites will again be stored securely and transferred back to the primary research centre.

The patient will then undergo traditional endocardial, and in appropriate cases, epicardial, mapping and ablation of ventricular tachycardia, using the techniques previously described ^{1-3,7,15}. Patient preparation on the day of the procedure will be as for any other clinical VT ablation. Ablation technique will depend on whether or not there is a documented 12 lead ECG of the patient's clinical VT and also whether or not the VT is haemodynamically tolerated (stable) or not (unstable). This will be decided by the operator and will follow usual practice for VT ablation.

We will use a multipolar mapping catheter, in order to create a high-density map and gain as detailed information as possible about the substrate. Multipolar catheters are used as standard of care for VT mapping and ablation in our institution and most other high-volume specialised centres. The 3D computational model will be merged with the traditional 3D electroanatomical map generated during the VT ablation. Particular care will be taken when mapping the points of interest from the computational prediction to assess their particular electrophysiological properties. This will allow us to assess variables such as wavefront directionality, amplitude and morphology to see if they have a particular signal which marks them as important in sustaining the VT circuit and therefore conferring their importance in predicting potential sites for ablation. By overlaying the computer generated model onto the invasive map, we will be able to corroborate the predicted model's findings with traditional mapping techniques.

Ablation technique will be as per standard of care and the order of ablation will be guided by standard invasive mapping. However if we ablate at an area which the MRI-model also predicted to be important, we will re-map the surrounding myocardium to see if there has been an effect of the electrophysiological properties of these distant sites following ablation of the predicted sites.. The computer model will not alter the extent of ablation and will not lead to ablation of any areas which wouldn't otherwise be ablated using traditional mapping.

The patients will be followed up as standard of care at 3, 6 and 12 months following their procedure with ICD interrogation, or in the case of absence of an ICD an extended ECG monitoring period. We will use this to assess frequency and duration of recorded arrhythmias time to recurrence of ventricular arrhythmia as well as frequency of therapy delivered by the device. We will also use data from their clinical consultation to evaluate their symptoms and response to the procedure including any adverse events.

STUDY FLOW CHART

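### Scar-wide maps are collected, but no planned outcome counts the important sites the model missed or compares predicted sites with non-predicted scar

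*Combined protocol and SAP*

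**What the plan says.** The first aim in section 4 is to assess how accurate the MRI-based model is. Section 4.2 turns this into an outcome on the degree of validation, asking "to see if the predicted sites match those sites which would have been determined as important from invasive mapping". The accuracy objective in section 4.1 is also worded from the predicted sites. Section 5 plans to overlay the model on the invasive map to corroborate its findings. None of these places gives an accuracy statistic, a matching distance or a denominator.

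The second outcome in section 4.2 is "Qualification of the electrophysiological characteristics of those sites which the computational model predicted". Section 5 states the question behind it: "to see if they have a particular signal which marks them as important in sustaining the VT circuit". Section 2 adds the hope that "we may learn which signals may indicate a critically important part of the VT circuit which traditional electroanatomical maps may miss".

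Data collection is wider than these outcomes. Section 4.1 has a separate objective, "To assess the ventricular scar characteristics in patients with scar-dependent VT using high-definition invasive mapping". Section 5 plans a high-density map with a multipolar catheter, and section 7.3.3 collects voltage, activation time, amplitude, directionality and morphology at a range of endocardial and epicardial points. The third outcome in section 4.2 looks at distant sites, but as change after ablation and not as a reference group.

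Section 8.1 foresees important areas that the model does not predict and says they will still be ablated. It does not plan to count them. Section 7.2.1 states that at least 20 patients are enough to judge whether the modelling is accurate.

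**The concern.** Two analyses that the stated questions need are not planned.

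- **Missed sites.** Agreement between two sets of sites has two directions: how many predicted sites are confirmed, and how many important sites were predicted. The wording starts from the predictions each time. If only the first proportion is reported, a model that names a few easy sites correctly scores well however much it leaves out. Because no measure is fixed, the direction could also be chosen after the results are seen.
- **Reference group.** A signal can mark predicted sites as important only if it is less common in comparable tissue that was not predicted. Section 1 lists low voltage, fractionation and late potentials as features of arrhythmogenic substrate in general, so finding them at predicted sites would not show that they separate those sites from the rest of the scar. Section 2 names this very discrimination as the weakness of current mapping: "The ability to identify arrhythmogenic from non-arrhythmogenic areas within the same scar is limited".

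What is at stake is the study's conclusion. Section 2 says that an accurate model would advance planning of ablation by computer, so a one-way match could be read as stronger support than it is. The model does not alter the ablation (sections 5 and 8), so patients in this study are not directly affected.

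**Working it through.** **No plan figure to reproduce.** The documents give no target accuracy, expected match, precision, alpha or power. The only relevant number is the minimum of 20 patients in section 7.2.1, which has no derivation.

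**Missed sites.** Let P be the number of predicted sites, I the number of invasively important sites, and m the proportion of predicted sites confirmed. Assume one-to-one matching, so that each important site confirms at most one predicted site. Then:

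- confirmed sites = m × P
- share of important sites captured = m × P / I = m × (P/I)

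The identity is exact under that assumption. The ratio P/I is not in the documents, so a range is shown. For counts, take P = 40 (assumed: 2 sites in each of 20 patients) and m = 0.80, which gives 32 confirmed.

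| P/I (assumed) | I = 40 / ratio | Captured = 0.80 × ratio | Missed = I − 32 |
|---|---|---|---|
| 1.25 | 32 | 100% | 0 |
| 1 | 40 | 80% | 8 |
| 0.5 | 80 | 40% | 48 |
| 0.25 | 160 | 20% | 128 |

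A ratio of 1.25 is the largest compatible with m = 0.80, because the confirmed sites (0.80 × P) cannot exceed I. The same 80% match thus covers everything from no missed sites to four in five missed.

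**Reference group.** No arithmetic applies here, so the texts are set side by side.

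| Place | What it covers | Comparison stated |
|---|---|---|
| 4.2, second outcome | Electrograms at predicted sites | None |
| 5 | Whether a signal marks those sites as important | None |
| 4.1, scar objective | Scar in general | None |
| 4.2, third outcome | Distant sites, change after ablation | Before and after, not predicted against non-predicted |
| 7.3.3 | Points from various locations | Collection only |

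The points for a comparison are likely to exist; the comparison is not stated. Section 5 also says that predicted points will be mapped with particular care, so sampling is likely to be denser there. An unadjusted comparison would inherit that difference.

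**The case against.** The strongest reply is that the plan is broader than this reading. Accuracy, validation and match are not defined, so the one-way reading is partly an inference. The overlay in section 5 could show unpredicted important areas as readily as matches. This stands as a limit on the claim: the plan does not exclude two-way reporting, but it does not commit to it either.

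A reader might infer that electrograms are recorded only at predicted sites. The documents do not support that. Sections 4.1, 5 and 7.3.3 provide for scar-wide mapping; only the second outcome is confined to predicted sites.

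A reader might also infer that missed sites would refute the model, since section 1 says "An algorithm is used to predict optimal ablation sites to terminate all possible VT circuits in this model heart" and that "all future potential ventricular tachycardias supportable by the substrate in its current form should also be avoided". That goes too far. This is background about circuits in the model heart, not a claim to predict every area that invasive mapping would call important. Where only substrate mapping defines importance, an unpredicted area may be an over-call by the reference, given the limit that section 2 admits. The model may also target the same circuit at another place.

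A third inference, that a high match could be due largely to chance, cannot be sized. It depends on how much of the mapped scar lies near an important site and on the matching rule, and the documents give neither. No chance-agreement figure is claimed.

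Finally, the second aim in section 4 is descriptive, and description alone satisfies it. But the section 5 question about a marking signal is comparative and needs a reference.

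**Conclusion.** The point holds in a limited form. Scar-wide data are collected, but no planned outcome counts important sites that the model missed, and none compares predicted sites with non-predicted scar. As written, a high match could be presented as validation without showing what was missed, and the question about a distinguishing signal cannot be answered.

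The size is not estimable from the documents. The span of 20% to 100% captured at an 80% match rests on one-to-one matching and on assumed ratios of predicted to important sites. It shows how little a one-way match says about completeness and is not a forecast. The share of patients in whom only substrate mapping would define importance is also not given. This is a cheap improvement to the analysis plan; it is not a flaw in data collection or in patient care.

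**What to change.** Add to sections 4.2 and 5, before analysis:

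1. Define an invasively important site separately for each mapping method (activation, entrainment, pace-mapping, substrate), and fix a matching distance. Without this definition the second proportion below has no denominator.
2. Report both the proportion of predicted sites confirmed and the proportion of invasively important sites predicted. Show primary and secondary sites separately, because secondary sites are predicted for the heart after virtual ablation. List predicted sites in unmapped regions as not assessable. For each missed site, give the distance to the nearest predicted site. Interpret missed sites cautiously where only substrate mapping defines importance.
3. For the second outcome, compare electrogram features at predicted sites with non-predicted scar points from the same patient's map, allowing for clustering within patient and for denser sampling at predicted sites.

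A benchmark that places the same number of sites at random in each patient's mapped scar is optional.

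Cost: added analysis text and code, plus some work to label important sites, segment scar and register the model to the map. Section 7.3.3 lists the map points but no importance label, so the labelling is additional. No extra procedure or patient data is needed. Unmapped regions cannot be scored, and the accuracy figure may look less favourable.

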7.3.3 Data collection tool

Each patient enrolled into the study will have a unique study trial ID number. This will allow the de-identification of all subsequent data associated with that patient. All subsequent data collection will be

transcribed next to this trial ID number in electronic format, through Microsoft Excel spreadsheets. There will be an electronic link document which will contain the patient identifiable information and the trial ID numbers, but no other data. This will be electronic and kept secure on password protected computers at St George's University, to which only the study investigators will have access. The link document will be kept until the results of the study have been analysed and written up. We anticipate that this will be complete within 3 years. The patient's consent will be kept in a locked area in the University.

Routine baseline demographics, risk factors and investigation results such as the patient's ECG and echocardiogram findings will be collected, de-identified and added to the Excel sheet. Primary data generated by the study will include the 3D computational model generated from the patient's cardiac MRI as well as data from the VT ablation including the baseline ECG, and electrograms during tachycardia and baseline rhythm. Individual data points from various endocardial and epicardial points will be collected by the mapping catheters which will contain information such as voltage, activation time, electrogram amplitude, directionality and morphology. Pacemaps and entrainment maps will be collected if these techniques are used. This data is generated by the cathlab software – Precision and Carto and will be de-identified, then transferred via USB stick to the password-protected excel spreadsheet with the appropriate trial ID number.

The data generated from the study will be stored for the duration of the study (3 years) and then archived onto secure, password-protected hard-drives. Paper documents will be archived with Iron Mountain for 5 years.

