8.1 Assessment and management of risk

The research protocol is predominantly within established standards for patients presenting with sustained monomorphic scar-dependent ventricular tachycardia. Undergoing a cardiac MRI and endocardial / epicardial

mapping and ablation for patients unresponsive to, intolerant of, or unwilling to use anti-arrhythmic therapy, is within the scope of international guidelines for these patients. Therefore, the protocol incurs no additional procedure for the patient. The extra time spent with co-registration of the computationally-generated virtual heart with the invasively-acquired 3D EAM, the extra mapping of the *in silico* predicted targets and remapping after ablation of the predicted sites, will mean that the procedure is only minimally extended beyond standard care, and by no more than a maximum of 10% of the usual duration. We propose that this does not generate a particular increase in risk compared to a standard VT ablation beyond the increased chance of complication from general anaesthetic. The overall goal of the ablation will remain the same whether the patient is included in the study or not – to render the patient non-inducible to VT. We will not ablate any area of the heart that wouldn't warrant it during a standard VT ablation and no area that is deemed important will be left un-ablated if the model does not predict it to be important. Therefore there is no expectation that they will be at higher risk of recurrence from participating in this study.

The data collection and sharing with Johns Hopkins University generates data protection requirements which will be met in accordance to the Data Protection Act of 2018. All patient information will be stored securely on restricted-access University storage and will be transferred securely only to the research team members directly involved in the study.

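### The first-listed outcome judges site agreement by overlay, with no scoring rule, merge-error measure or chance level, so it cannot separate model accuracy from chance proximity or merge error

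*Combined protocol and SAP*

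**What the plan says.** The first aim in section 4 is the accuracy of the model. Section 4.1 repeats it as an objective: "To assess the accuracy of the *in silico* predicted sites when compared to invasively obtained electrophysiological data". The first of the four outcomes in section 4.2 is a degree of validation, namely "to see if the predicted sites match those sites which would have been determined as important from invasive mapping".

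The method is in section 5: "The 3D computational model will be merged with the traditional 3D electroanatomical map generated during the VT ablation". Agreement is then read from the result: "By overlaying the computer generated model onto the invasive map, we will be able to corroborate the predicted model's findings with traditional mapping techniques".

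The merge is mentioned again in section 8.1, but only for the procedure time it adds: "The extra time spent with co-registration of the computationally-generated virtual heart with the invasively-acquired 3D EAM". Section 7.3.3 describes point-level catheter data "which will contain information such as voltage, activation time, electrogram amplitude, directionality and morphology". That list is illustrative, and it names neither a merge error nor a distance between sites.

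None of the supplied text gives a match distance or segment scheme, a scoring rule, a limit on merge error, or a chance comparator. The flow chart is not shown, but the text does not refer to it for any such rule.

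**The concern.** Two things other than model quality affect how well the sites appear to agree.

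- **Merge error.** The model geometry comes from an MRI taken before the procedure, and the map is built by catheter during it. Aligning them shifts every predicted site by an amount that belongs to the alignment. If the shift is not measured, a miss cannot be assigned to the model or to the merge.
- **Chance proximity.** The model works from scar and grey zone, and invasive substrate mapping looks for abnormal signals in the same tissue. Sites placed anywhere in that scar will sometimes fall near an invasively important one.

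With no rule set in advance, the plan also leaves open choosing the tolerance with both maps in view. The conclusion on the study's first aim is at stake. The third outcome is touched too: re-mapping is triggered "if we ablate at an area which the MRI-model also predicted to be important", which needs the same unstated notion of being in the same place.

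**Working it through.** **The plan's own figure.** There is none to reproduce. Section 7.2.1 gives at least 20 patients with no expected agreement, precision or distance. All values below are assumptions used to show the mechanism.

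**1. Perfect model, merge error only.** Assume the error is normal and equal on two axes along the wall, with SD s = 4 mm (range 3-5). The distance is then Rayleigh and P(match within r) = 1 − exp(−r²/2s²).

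- s = 4, r = 5: 1 − exp(−25/32) = 54%. For s = 5 and s = 3: 39% and 75%.
- s = 4, r = 10: 1 − exp(−100/32) = 96%. For s = 5 and s = 3: 86% and 99.6%.

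**2. Random sites.** Assume sites uniform over scar area A with k important invasive sites. Ignoring edges, P(match within r) = 1 − (1 − πr²/A)^k. At r = 10 mm, πr² = 314 mm², so A = 60 cm² and k = 5 give 1 − (1 − 314/6000)^5 = 23.6%. The edge-adjusted values come from 400,000 random draws per setting on a flat circular scar.

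| A (cm²) | k | 10 mm, formula | 10 mm, with edges | 15 mm, formula | 15 mm, with edges |
|---|---|---|---|---|---|
| 40 | 5 | 33.6% | 29.9% | 62.2% | 53.6% |
| 60 | 5 | 23.6% | 21.5% | 46.6% | 40.8% |
| 80 | 5 | 18.2% | 16.7% | 37.0% | 33.0% |
| 40 | 2 | 15.1% | 13.4% | 32.2% | 26.9% |
| 60 | 2 | 10.2% | 9.2% | 22.2% | 19.0% |
| 80 | 2 | 7.7% | 7.1% | 16.9% | 14.9% |

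At 5 mm the formula gives 5-9% with k = 5 and 2-4% with k = 2.

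**3. What match distance would be adequate?** The mean merge error is m = s√(π/2), which is 5.0 mm for s = 4. In terms of m, the perfect-model rate is 1 − exp(−(π/4)(r/m)²).

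- r = m: 1 − exp(−π/4) = 54%. A distance merely equal to the typical error still makes a perfect model look poor.
- r = 2m: 1 − exp(−π) = 96%, whatever m is.

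For s = 4, 2m is 10 mm. A perfect model then scores 96%, against about 7-30% for random placement with edges allowed for.

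**The case against.** The strongest reply is that the plan has been read too narrowly. It calls no outcome main or primary, and it speaks of a degree of validation, so a graded or distance-based assessment would fit its words. A reader might infer that the endpoint is a yes/no count of matches, or that the tolerance will be picked after looking. Neither is stated. What stands is that no scoring rule of any kind is given.

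A second reply is that every millimetre, area and site count above is assumed, and that the alarming end needs a loose tolerance. This is fair. A reader might infer that a random model would commonly look moderately good, or that no match rate could be interpreted. The figures do not support that. At 10 mm the two are clearly separated, and with 80 cm² of scar and two targets random placement reaches only about 15% even at 15 mm.

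Third, this is a small single-centre study in which the model does not change what is ablated (sections 5, 8 and 8.1). A misleading agreement figure would affect interpretation, not treatment. That limits the weight of the point. It does not remove it, because accuracy is the study's first question.

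**Conclusion.** The point holds in limited form. Overlay as described cannot tell an accurate model from chance proximity within the same scar, nor a model miss from a merge error. The absence of a distance, a scoring rule, a merge-error measure and a chance level is plain from the text.

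The size is illustrative only. Under the assumed 4 mm SD, moving the tolerance from 5 to 10 mm takes a perfect model from 54% to 96%. At 10 mm, chance agreement runs from about 8% to 34% by the simple formula, depending on scar area and number of targets. These values rest on isotropic error along the wall, uniform random placement and two to five targets, none of which the documents supply.

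This is a cheap improvement worth making, because it changes what the study can conclude about accuracy. It does not show that the reported agreement will be wrong.

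**What to change.** In sections 4.2 and 5:

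1. Make the accuracy measure the distance in mm from each predicted site to the nearest invasively important site. Report also the distance from each invasive site to the nearest predicted site, so that sites the model missed count.
2. Beside these, report the same distances and any match rates for an equal number of sites placed at random on that patient's own scar, using the scar already segmented for the model. Because the invasive sites are held fixed, the benchmark also allows for distances shrinking as more of them are marked.
3. If a match rate is reported, fix the distance before any study overlay is scored, at about twice an assumed mean merge error stated in advance. Show the rate at two other distances. Using an assumed value avoids having to wait for the study's own merges.
4. Report each patient's merge error, noting that surface-to-surface distance does not capture sliding or rotation along the wall.

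The cost is protocol wording and some offline work to export site coordinates and scar surfaces in a common frame; section 7.3.3 does not name these items explicitly. It needs no extra patient procedure and does not change the ablation. The match rate may look less favourable beside its chance level.
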